## Clinical Investigation Plan

	

22. Aortic root angulation > 70°.

23. Currently participating in an investigational drug or device study.

24. Active bacterial endocarditis within 6 months prior to the index procedure.

25. Bulky calcified aortic valve leaflets in close proximity to coronary ostia.

26. Non-calcified aortic annulus.

27. Iliofemoral vessel characteristics that would preclude safe insertion of the FlexNav™ delivery system with or without an arterial introducer sheath such as severe obstructive calcification, or severe tortuosity.

28. In the judgment of the investigator, a condition that could limit a patient's ability or willingness to participate in the study, comply with study required testing and/or follow-up visits or that could impact scientific integrity of the study

--	--

## Statistical Analysis Plan

### 1.0 SYNOPSIS OF STUDY DESIGN

#### 1.1 Purpose of the Statistical Analysis Plan

This statistical analysis plan (SAP) is intended to provide a detailed and comprehensive description of the planned methodology and analysis to be used for the protocol [REDACTED] FlexNav EU CE Mark clinical study. [REDACTED]

#### 1.2 Clinical Investigation Objectives

The primary objective of the FlexNav EU study is to characterize the safety of the second-generation Portico FlexNav Delivery System.

#### 1.3 Clinical Investigation Design

The FlexNav EU study is a prospective, multi-center, single-arm investigational study and will include up to 200 high or extreme risk patients with symptomatic, severe native aortic stenosis who meet eligibility criteria for Portico™ Transcatheter Aortic Heart Valve implantation via a transfemoral access approach. Clinical investigation visits will occur at baseline, implant procedure, discharge, 30 days, 6 months and 12 months post-implantation for enrolled subjects. Thirty-day safety outcomes data for the first 73 subjects to undergo an attempted Portico™ valve implant using the FlexNav™ Delivery System will be summarized to support commercialization of the FlexNav™ Delivery System and Loading System in Europe.

#### 1.4 Endpoints

##### 1.4.1 Primary Endpoint

The primary safety endpoint for this study is VARC-2 defined major vascular complications at 30 days post index procedure.

##### 1.4.2 Descriptive Endpoints

The following descriptive endpoints at 30 days will be reported in the CE Mark submission:

- Non-hierarchical composite of all-cause mortality, disabling stroke, life threatening bleeding requiring blood transfusion, acute kidney injury requiring dialysis, or major vascular complications at 30 days from the index procedure.
- All-cause mortality at 30 days from the index procedure.
- Disabling stroke at 30 days from the index procedure.
- Non-disabling stroke at 30 days from the index procedure.
- Life threatening bleeding requiring blood transfusion at 30 days from the index procedure.
- Major bleeding at 30 days from the index procedure.
- Acute kidney injury at 30 days from the index procedure.
- Minor vascular complication rates at 30 days from the index procedure.

## Statistical Analysis Plan

- Permanent pacemaker insertion at 30 days from the index procedure.
- Paravalvular Leak (PVL) at 30 days from the index procedure.
- NYHA functional classification at 30 days from the index procedure.
- KCCQ Quality of Life (QOL) score from baseline to 30 days from the index procedure.
- Technical device success defined as successful vascular access, delivery and deployment of the Portico Valve; retrieval with the delivery system and correct positioning of a single valve in the proper anatomical location.

Additional descriptive endpoints at one year include:

- Composite of all-cause mortality or disabling stroke at one year from the index procedure.
- All-cause mortality at one year from the index procedure.
- Disabling stroke at one year from the index procedure.
- Non-disabling stroke at one year from the index procedure.
- Paravalvular Leak (PVL) at one year from the index procedure.
- KCCQ Quality of Life (QOL) score from baseline and one year from the index procedure.
- NYHA functional classification at one year from the index procedure.

## 2.0 ANALYSIS CONSIDERATIONS

### 2.1 Analysis Population

### 2.2 Statistical Methods

#### 2.2.1 Descriptive Statistics for Continuous Variables

For continuous variables (e.g., age, etc.), results may be summarized with the numbers of observations, means, and standard deviations, with quartiles, minimums, maximums, and 95% confidence intervals for the means.

#### 2.2.2 Descriptive Statistics for Categorical Variables

For categorical variables (e.g. gender, etc.), results may be summarized with subject counts and percentages/rates, and where specified in the table mockups, with exact 95% Clopper-Pearson confidence intervals.

#### 2.2.3 Survival Analyses

Survival analysis will be conducted to analyze time-to-event variables. Subjects without events will be censored at their last known event-free time point. Survival curves will be constructed using Kaplan-Meier estimates.

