### 4.2 Descriptive Endpoint(s)

A selection of descriptive endpoints including valve performance parameters, clinical function assessments and adverse events defined according to VARC 2 criteria will be assessed at 30 days and at 12 months as defined below. All descriptive endpoints will be summarized separately using descriptive statistics.

Descriptive endpoints to be assessed at 30 days and included in the CE Mark submission:

- Non-hierarchical composite of all-cause mortality, disabling stroke, life threatening bleeding requiring blood transfusion, acute kidney injury requiring dialysis, or major vascular complications at 30 days from the index procedure.
- All-cause mortality at 30 days from the index procedure.
- Disabling stroke at 30 days from the index procedure.
- Non-disabling stroke at 30 days from the index procedure.
- Life threatening bleeding requiring blood transfusion at 30 days from the index procedure.
- Major bleeding at 30 days from the index procedure.
- Acute kidney injury at 30 days from the index procedure.
- Minor vascular complication rates at 30 days from the index procedure.
- Permanent pacemaker insertion at 30 days from the index procedure.
- Paravalvular Leak (PVL) at 30 days from the index procedure.
- NYHA functional classification at 30 days from the index procedure.
- KCCQ Quality of Life (QOL) score from baseline to 30 days from the index procedure.
- Technical device success defined as successful vascular access, delivery and deployment of the Portico Valve; retrieval with the delivery system and correct positioning of a single valve in the proper anatomical location.

Additional descriptive endpoints to be assessed at one year but not included in the CE Mark submission:

- Composite of all-cause mortality or disabling stroke at one year from the index procedure.
- All-cause mortality at one year from the index procedure.
- Disabling stroke at one year from the index procedure.

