#### 3.5 Descriptive Endpoints

The analyses for the descriptive endpoints listed in Section 1.4.2 will be performed using the methods described in Section 2.2 for the analysis population described in Section 2.1.

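### If the SAP's Kaplan-Meier rule is applied to one-year stroke, as its wording allows, stroke-free deaths are censored and stroke incidence is slightly overstated

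*SAP*

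**What the plan says.** SAP 2.2.3 applies survival analysis to time-to-event variables. It states "Survival curves will be constructed using Kaplan-Meier estimates" and gives one censoring rule: "Subjects without events will be censored at their last known event-free time point". The readable text does not mention death as a competing event and names no cumulative incidence estimator.

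SAP 1.4.2 lists stroke at one year as endpoints in their own right, for example "Non-disabling stroke at one year from the index procedure", with disabling stroke listed in the same way. All-cause mortality and a composite of death or disabling stroke are listed alongside them.

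SAP 3.5 makes the link to a method: "The analyses for the descriptive endpoints listed in Section 1.4.2 will be performed using the methods described in Section 2.2". Section 2.2 also contains 2.2.2, under which "results may be summarized with subject counts and percentages/rates". No readable sentence says which endpoint takes which method. Protocol 4.2 says only "All descriptive endpoints will be summarized separately using descriptive statistics", and it places the one-year endpoints outside the CE Mark submission.

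**The concern.** For the stroke endpoint, a subject who dies stroke-free is a subject without the event. The rule in 2.2.3, read as written, therefore censors that subject at death. Censoring treats the subject as someone who could still have a stroke later. One minus Kaplan-Meier then estimates stroke risk in a hypothetical population in which nobody dies, whereas the report presumably wants the proportion of treated subjects who have a stroke. The error goes one way only, grows with mortality, and is not removed by enrolling more subjects or shown by a confidence interval.

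All-cause mortality and the death-or-disabling-stroke composite are unaffected, because death is itself an event there. What is at stake is the accuracy of the two one-year stroke rates, if they are read off a Kaplan-Meier curve.

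**Working it through.** There is no plan figure to reproduce: the readable documents state no expected one-year stroke rate or mortality.

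**Inputs**
- Estimator and censoring rule: SAP 2.2.3.
- Sample size: up to 200, single arm (SAP 1.3). Follow-up: 12 months (Protocol 3.3).
- One-year stroke risk on the Kaplan-Meier scale, S: **assumed** 2%, 4%, 6%.
- One-year mortality, D: **assumed** 10% to 30%. The eligibility criteria describe surgical risk, which is not one-year mortality after transcatheter implantation.

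**Constant hazards.** Let ls = −ln(1 − S) and ld = −ln(1 − D). Then
- one minus Kaplan-Meier with deaths censored = 1 − exp(−ls) = S;
- cumulative incidence = ls/(ls + ld) × [1 − exp(−(ls + ld))].

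Example with S = 4%, D = 20%: ls = 0.0408, ld = 0.2231, sum = 0.2640. The bracket is 1 − 0.96 × 0.80 = 0.232. Cumulative incidence = (0.0408/0.2640) × 0.232 = 3.59%. Kaplan-Meier gives 4.00%, an excess of 0.41 points.

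**Early strokes.** The same formula is applied in two intervals, with an assumed 70% of the stroke hazard and 25% of the death hazard in the first 30 days.

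Results for S = 4%:

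| Mortality D | Cumulative incidence, constant hazards | Excess (points) | Cumulative incidence, early strokes | Excess (points) |
|---|---|---|---|---|
| 10% | 3.80% | 0.20 | 3.89% | 0.11 |
| 15% | 3.69% | 0.31 | 3.83% | 0.17 |
| 20% | 3.59% | 0.41 | 3.77% | 0.23 |
| 25% | 3.48% | 0.52 | 3.71% | 0.29 |
| 30% | 3.37% | 0.63 | 3.65% | 0.35 |

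**Extremes of the assumed range**
- S = 2%, D = 10%: 1.90% (excess 0.10) under constant hazards; 1.94% (excess 0.06) with early strokes.
- S = 6%, D = 30%: 5.06% (excess 0.94) under constant hazards; 5.47% (excess 0.53) with early strokes.
- In relative terms, 5% to 19% under constant hazards and 3% to 10% with early strokes.

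Solved the other way under constant hazards, a true incidence of 5% would be reported as 5.27% at 10% mortality and 5.75% at 25%.

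**Simulation check** (200 subjects, 4,000 runs, S = 4%, D = 20%, constant hazards, no other censoring): mean one minus Kaplan-Meier 4.04%, against 3.62% of subjects with an observed stroke. The standard deviation of the Kaplan-Meier estimate is 1.5 points. For scale, the exact 95% interval for 8 strokes in 200 subjects is 1.7% to 7.7%.

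**At 30 days** the effect is negligible: with an assumed stroke risk of 3% and mortality of 2% to 6%, the excess is 0.03 to 0.09 points.

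**The case against.** A reader might infer three stronger things, and the documents support none of them.

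- **That the SAP commits to Kaplan-Meier for stroke with deaths censored.** Section 2.2.3 names neither stroke nor death. Section 3.5 points to all of 2.2, and stroke at one year could be reported as a simple percentage under 2.2.2. Kaplan-Meier may be meant only for mortality and the composite. The item directly after 2.2.3 is not shown, the text of 2.1 and 2.9 is not readable, and the table mock-ups are not supplied, so an assignment or a rule for death may exist there. This objection stands, and the point is therefore conditional.
- **That one-year mortality is known to be high.** Eligibility rests on surgical risk, and Protocol 5.3.3 excludes subjects with a non-cardiac life expectancy under 12 months. No one-year rate is given. This also stands: the rates used above are assumptions.
- **That the stroke rates could not be reconciled with crude counts.** SAP 3.2 separately reports adjudicated events as counts and as percentages of enrolled subjects, so a reader could compare them directly.

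It is also fair to say that the bias is well inside sampling error and that no test, threshold or submission decision in the readable text depends on one-year stroke.

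The simple percentage is not a complete answer, however. It equals the cumulative incidence only with complete follow-up. Subjects with an implant attempt but no Portico valve leave after 30 days (Protocol 5.4 and 6.2.3), and withdrawn subjects contribute only vital status, if they agree (Protocol 5.5). Cumulative incidence estimation handles both this censoring and death.

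**Conclusion.** The point holds conditionally and is minor. The one readable survival rule in the SAP, applied to a non-fatal endpoint such as one-year stroke, gives an estimate that is too high, and nothing readable excludes that use. The size is about 0.1 to 0.9 percentage points under constant hazards, and about 0.06 to 0.5 points if strokes cluster early. Both ranges rest on assumed stroke risk of 2% to 6% and assumed mortality of 10% to 30%. At the maximum enrolment of 200, sampling variation (standard deviation about 1.5 points at stroke 4% and mortality 20%) is larger than the bias. The affected endpoints are descriptive and outside the CE Mark submission; the 30-day primary endpoint is not the subject of this point. It merits a change because a better estimator uses the same data at almost no cost.

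**What to change.** In SAP 2.2.3, state that Kaplan-Meier is used for all-cause mortality and for composites that include death. State that disabling stroke, non-disabling stroke and any other non-fatal time-to-event endpoint are estimated by the cumulative incidence function (Aalen-Johansen), with death before the event as a competing event and subjects who leave alive censored when they leave. If the unredacted SAP already assigns an estimator to one-year stroke and a rule for death, a cross-reference from 3.5 is enough.

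The cost is one SAP sentence. It needs no new data and no change to the design, sample size or primary endpoint, and the estimator is available in SAS 9.4, the software named in SAP 4.0.

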## Statistical Analysis Plan

[figure not shown]
### 2.2.4 Analyses in Response to COVID-19 Impact

As the Coronavirus Disease 2019 (COVID-19) pandemic has spread around the globe, the following analysis mechanism will be implemented to minimize the potential confounding effect from this emerging infectious disease for the study endpoints set forth in final report. In alignment with the guidance document “FDA Guidance on Conduct of Clinical Trials of Medical Products during COVID-19 Public Health Emergency” updated on 03-June-2020, additional consideration was given to the impact of the COVID-19 pandemic on the descriptive endpoint analyses for this study. As such, prespecified methods are included in the sections that follow to indicate the handling of any outcomes impacted by COVID-19 as well as efforts to minimize missing endpoint data during the COVID-19 pandemic. Specific analyses to address COVID-19 impacts are included in relevant subsections in Section 2.0 and Section 3.0.

## 2.3 Endpoint Analysis

[figure not shown]
### 2.3.1 Primary Endpoint

The primary safety endpoint for this study is VARC-2 defined major vascular complications at 30 days post index procedure.

## 2.4 Sample Size Calculations

The minimum sample size of 73 subjects is based

## Statistical Analysis Plan

### 2.5 Interim Analysis

No formal interim analyses are planned for this study.

### 2.6 Timing of Analysis

### 2.7 Study Success

### 2.8 Subgroups for Analysis

Subgroup analysis will be performed to examine the consistency of the primary endpoint across baseline risk categories.

### 2.9 Handling of Missing Data

### 2.10 Poolability Analysis

Poolability analysis may be performed

### 2.11 Multiplicity

## Statistical Analysis Plan

### 3.0 DESCRIPTIVE ENDPOINT AND ADDITIONAL DATA

#### 3.1 Baseline and Demographic Characteristics

The following baseline and demographic variables, including but not limited to: gender, age, medical history, procedural characteristics etc. will be summarized using descriptive statistics for the enrolled subjects.

#### 3.2 Adverse Events

All the adverse events, serious adverse events will be summarized for all subjects who enrolled in this study in terms the number of events, the percentage of subjects with events. All Clinical Events Committee (CEC) adjudicated adverse events will also be summarized for all subjects who enrolled in the study in terms of the number of events, the percentage of subjects with events. In addition, [REDACTED]

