14. Coronary and aortic angiogram (arteriograms of the lower abdominal aorta to the femoral arteries), with runoff if clinically indicated. Coronary and aortic angiogram performed up to 12 months prior to consent will be acceptable.
15. Adverse Event Assessment

Subjects must be screened for clinical investigation eligibility by a member of the study site's clinical investigation team (Principal Investigator and/or Research Coordinator) previously trained to the CIP, and if applicable will be entered into a site-specific screening log.

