### 5.4 Subject Enrollment

A patient will be considered enrolled in the study after completion of all of the following steps:

1. Signed informed consent is obtained.
2. Based on the screening assessments, it is determined that the subject meets all of the inclusion and none of the exclusion criteria.
3. Subject is approved by the Subject Selection Committee.
4. Portico implant attempt defined as insertion of the FlexNav™ Delivery System into the subject's vasculature.

The following terms will be used to describe potential study subjects:

- **Screen Failure:** Consented subjects who undergo study-specific testing and are found to have met exclusion criteria or not all inclusion criteria. Additionally, if a site disagrees with the Subject Selection Committee's final decision regarding risk classification the subject will not be eligible for enrollment in the study and will be considered a screen failure.
- **Pre-procedural Exclusion:** Consented subjects who undergo study-specific testing and meet study criteria but do not undergo a Portico implant attempt will not be considered enrolled and will be exited from the study without further follow up.
- **Enrolled:** These subjects will be considered enrolled in the study and will fall into one of the following categories:
  - **Attempted-to-Treat:** Subjects who undergo a Portico implant attempt but do not have a Portico valve implanted will be followed for 30 days post procedure for adverse events and then formally withdrawn from the study
  - **Implanted:** Subjects who have a Portico valve implanted will be followed according to the clinical investigation and will be included in the analysis population.
  - **CIP Deviations:** Subjects who have a Portico valve implanted and are later found to have met exclusion criteria or not all inclusion criteria. These subjects will be followed according to the clinical investigation and will be included in the analysis population.

Notification of enrollment to the Sponsor is considered to have occurred when the Sponsor has received the applicable CRF (Procedure Form).

To ensure enrollment balance across study sites, no investigational site will be permitted to enroll more than 20% of the analysis population.

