### 6.1 Baseline Assessments

#### 6.1.1 Baseline Laboratory and Clinical Tests

Patients who are deemed eligible for transfemoral implantation of a Portico™ valve using the FlexNav™ Delivery System will undergo a baseline visit within 14 days of the scheduled implant procedure (may occur on the day of, but prior to the implant procedure).

The following baseline data will be collected for all subjects prior to the index procedure.

1. Chest X-ray
2. Cardiovascular medications documentation (including dosage)
3. Modified Rankin Scale (mRS)
4. NIH Stroke Scale (NIHSS)
5. Barthel Index
6. Quality of Life Measures (SF-36, EQ-5D and KCCQ)
7. Mini Mental State Exam (MMSE-2:SV)
8. Six Minute Walk Test (6MWT)
9. Lab Measurements (Troponin or CK/CK-MB, INR if subject is on Coumadin or Warfarin or other anticoagulants/vitamin K antagonists in lieu of warfarin)
10. Adverse events assessment

Excluding the chest X-ray scan which is standard of care and will be conducted per hospital guidelines, all baseline assessments are considered study-related assessments.

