## 7.3 Adverse Event and Device Deficiency Reporting

### 7.3.1 Adverse Event Reporting

Safety surveillance and reporting starts as soon as the patient is consented into the clinical investigation. Safety surveillance and reporting will continue until the last 12-month follow-up visit has been performed, the subject is deceased, the subject concludes participation in the clinical investigation or the subject withdraws from the clinical investigation. All adverse event data, including deaths and device deficiency data, will be collected throughout the time period defined above and will be reported to the Sponsor on a CRF. Additional information with regard to an adverse event should be updated within the appropriate CRF.

Unchanged, chronic, non-worsening or pre-existing conditions are not AEs and should not be reported.

Adverse event reporting will include:

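### As far as legible, SAP 3.2 puts no onset cut on the general AE, SAE and CEC summaries, so events between consent and FlexNav insertion are counted with events after exposure.

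*SAP*

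**What the plan says.** **Start of collection.** Protocol 7.3.1: "Safety surveillance and reporting starts as soon as the patient is consented into the clinical investigation". The screening list (5.2.1) includes an "Adverse Event Assessment" and the baseline list (6.1.1) an "Adverse events assessment"; both visits precede the procedure. Protocol 7.3.1 narrows what counts: "Unchanged, chronic, non-worsening or pre-existing conditions are not AEs and should not be reported".

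**Start of enrolment.** The last of the four enrolment steps in Protocol 5.4 is "Portico implant attempt defined as insertion of the FlexNav™ Delivery System into the subject's vasculature". This is also first exposure to the investigational device. Consented subjects who meet the criteria but "do not undergo a Portico implant attempt will not be considered enrolled", and they leave the study without further follow-up.

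**Tabulation.** SAP 3.2 states that all AEs and SAEs "will be summarized for all subjects who enrolled in this study in terms the number of events, the percentage of subjects with events". The next sentence applies the same population and measures to all CEC-adjudicated events. A further sentence begins and is then blacked out.

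**Endpoints.** The primary endpoint (SAP 1.4.1) and the descriptive event endpoints (SAP 1.4.2) are timed from the index procedure.

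**The concern.** The population in SAP 3.2 is defined by an event (device insertion) that comes after the start of AE collection, and the counting rule does not reset the clock. Two things follow.

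- A new or worsening event between consent and insertion counts towards the AE and SAE figures although no study device was present. It also counts towards the CEC figures if it is of a type the committee adjudicates.
- The pre-procedure part is selective. A patient who has an event before the procedure and is later implanted contributes it. A patient whose event, or death, prevents the implant attempt is never enrolled and contributes nothing. The table is therefore neither a clean post-exposure account nor a complete pre-procedure one.

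The study's only stated objective is to characterize the safety of the delivery system, in a single arm. No control group shows the background rate, so overall AE and SAE percentages are likely to be read as describing what follows use of the device. A CEC summary counted from consent could also differ from an endpoint table counted from the procedure for the same event type, with no stated reason for the difference.

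**Working it through.** The plan gives no figure to reproduce. The check is first a comparison of the text, then illustrative arithmetic on stated assumptions.

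**Step 1: does a pre-exposure interval always exist?** Yes. Consent must precede transmission of data to the core laboratories or the Subject Selection Committee (Protocol 5.1). Committee approval must precede scheduling of the baseline visit (3.4.3). The baseline visit must precede the procedure (6.1.1).

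**Step 2: how long is it?** Protocol 6.2.3 encourages, but does not require, the procedure within 14 days of committee approval. The documents state no limit from consent to approval. The total interval W is therefore an assumption.

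**Step 3: share of observed time before exposure**, W / (W + T), where T is follow-up after the procedure:

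| Assumed W | T = 30 days | T = 365 days |
|---|---|---|
| 14 days | 14/44 = 32% | 14/379 = 4% |
| 28 days | 28/58 = 48% | 28/393 = 7% |
| 45 days | 45/75 = 60% | 45/410 = 11% |

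These would be shares of events only if the event rate were constant. Procedural complications cluster at and after the implant, so the pre-exposure share of events should be smaller. SAP 3.2 does not specify a table ending at day 30, and collection runs to 12 months (Protocol 7.3.1).

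**Step 4: effect on the percentage of subjects with any AE.** Let p be the probability of a post-procedure AE and q that of a pre-procedure AE, both assumed and taken as independent. The tabulated percentage is 1 − (1 − p)(1 − q). Extra subjects among 73 (the stated minimum sample) are 73 × (1 − p) × q.

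| q | p = 30%: tabulated (extra of 73) | p = 60%: tabulated (extra of 73) |
|---|---|---|
| 2% | 31.4% (1.0) | 60.8% (0.6) |
| 5% | 33.5% (2.6) | 62.0% (1.5) |
| 10% | 37.0% (5.1) | 64.0% (2.9) |
| 20% | 44.0% (10.2) | 68.0% (5.8) |

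The documents give neither p nor q. The higher p is, the less the subject percentage moves, although event counts still rise by every pre-procedure event.

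**Step 5: effect on the endpoints.** None. An endpoint timed from the index procedure cannot take in an earlier event.

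**The case against.** **Part of the text is not visible.** The end of SAP 3.2 is blacked out, the content of SAP 2.1 and 2.6 is not shown, and the table mock-ups mentioned in SAP 2.2.2 are not available. A split by onset could sit in any of these. This stands as a limit, and the point is made only as far as the text is legible. However, the two counting sentences in SAP 3.2 are complete and name their own population. The blacked-out sentence opens as an addition to them, not as a restriction.

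**The pre-procedure residue may be small.** Several serious events bar enrolment because the exclusions look back from the index procedure: ST-elevation infarction or a percutaneous intervention within 30 days, stroke or TIA within 6 months, and upper GI bleeding within 3 months. Stable pre-existing disease is not an AE. The investigator also records device relationship for each event (Protocol 7.2), so related events can be separated. All of this stands and lowers the likely impact. It does not change the all-AE and all-SAE percentages, which remain mixed.

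**Stronger readings that the documents do not support.**

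- A reader might infer that the safety endpoints for the CE Mark submission are contaminated. They are not, because they start at the procedure. SAP 3.2 is a general AE summary and is not labelled a device safety table.
- A reader might take 32-60% as the share of events arising before exposure. It is a share of assumed time, in a 30-day table that SAP 3.2 does not specify.
- A reader might infer that comparison with pooled US data is compromised. The documents do not give the US consent-to-procedure interval, and Protocol 3.2 speaks of pooling 30-day safety outcomes. No legible text says that the all-AE table is pooled.
- Particular examples are also unsafe. A screening CT may predate consent by up to 12 months, so a contrast reaction may fall before AE collection. Heart-failure admission is not a listed endpoint, and the CEC's event list is in a charter that is not available here.

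**Conclusion.** The point holds as a defect in a stated counting rule. Collection from consent, enrolment at insertion, and tabulation of all events in enrolled subjects together put unexposed and exposed time in the same general AE, SAE and CEC summaries, with a selective pre-procedure part. This rests on a literal reading of the legible text; a split in the hidden text cannot be ruled out.

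The primary and descriptive event endpoints are unaffected. The effect on the general summaries cannot be sized from the documents. Under the assumptions in Step 4 it runs from less than one to about ten extra subjects of 73, and the exclusions anchored to the procedure date suggest that serious pre-procedure events would be few. It is worth correcting before analysis because the correction is cheap and the percentages describe safety in a study with no control arm.

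**What to change.** In SAP 3.2:

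1. Restrict the main AE, SAE and CEC summaries to events with onset at or after the start of the index procedure, shown for 0-30 days and 31 days-12 months. Starting at the procedure matches the time origin of the endpoints. State the denominator for the later window, since subjects with an attempt but no Portico valve leave the study after 30 days (Protocol 5.4).
2. List events from consent to procedure start in a separate table for all consented subjects, including those who never reach an implant attempt.
3. If the blacked-out text or the table mock-ups already make this split, say so in the two counting sentences.

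The cost is one flag derived from onset date and procedure date, one extra table, and the wording. Protocol 11.4 already provides for CRF data on everyone who signs consent, so no new data are needed.
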